15.4 Rituximab (Rituxan®, C2B8)

Refer to package insert for complete, up-to-date information.

- 15.41 **Background**: rituximab is a monoclonal antibody directed against the CD20 antigen on B-lymphocytes. CD20 regulates cell cycle initiation; and, possibly, functions as a calcium channel. rituximab binds to the antigen on the cell surface, activating complement-dependent cytotoxicity; and to human Fc receptors, mediating cell killing through an antibody-dependent cellular toxicity.
- 15.42 **Formulation**: Commercially available for injection, solution [preservative free]: 10 mg/mL (10 mL, 50 mL) [contains Polysorbate 80].
- 15.43 **Preparation, storage, and stability**: Refer to package insert for complete preparation and dispensing instructions. Store vials at refrigeration temperature do not freeze or shake. Protect vials from direct sunlight. Withdraw the necessary amount of rituximab and dilute to a final concentration of 1-4 mg/mL with 0.9% NaCL or D₅W. Gently invert the bag to mix the solution; do not shake. Solutions for infusion are stable at 2°C to 8°C for 24 hours and at room temperature for an additional 24 hours.
- 15.44 **Administration:** Do not administer I.V. push or bolus. Refer to treatment section for specific infusion instructions. Suggested administration guidelines are:

 Initial infusion: Start rate of 50 mg/hour; if there is no reaction, increase

the rate by 50 mg/hr every 30 minutes, to a maximum of 400 mg/hour. Subsequent infusions: If patient did not tolerate initial infusion follow initial infusion guidelines. If patient tolerated initial infusion, start at 100 mg/hour; if there is no reaction; increase the rate by 100 mg/hour every 30 minutes, to a maximum of 400 mg/hour.

Note: If a reaction occurs, slow or stop the infusion. If the reaction abates, restart infusion at 50% of the previous rate.

Accelerated infusion rate (90 minutes): Accelerated infusion rate is not an option for cycle 1. It is an option in cycle 2 and beyond for patients who have had a mild reaction and cannot yet be transitioned to rituximab and hyaluronidase human. For patients with previously untreated follicular NHL and diffuse large B-cell NHL who are receiving a corticosteroid as part of their combination chemotherapy regimen, have a circulating lymphocyte count <5000/mm³, or have no significant cardiovascular disease. After tolerance has been established (no grade 3 or 4 infusion-related event) at the recommended infusion rate in cycle 1, a rapid infusion rate may be used beginning with cycle 2. The daily corticosteroid, acetaminophen, and diphenhydramine are administered prior to treatment, then the rituximab dose is administered over 90 minutes, with 20% of the dose administered over the first 30 minutes and the remaining 80% is given over 60 minutes. If the 90-minute infusion in cycle 2 is tolerated, the same rate may be used for the remainder of the treatment regimen (through cycles 6 or 8).

15.45 Pharmacokinetic information:

Duration: Detectable in serum 3-6 months after completion of treatment; B-cell recovery begins ~6 months following completion of treatment; median B-cell levels return to normal by 12 months following completion of treatment

Distribution: RA: 3.1 L; GPA/MPA: 4.5 L

Absorption: Immediate and results in a rapid and sustained depletion of circulating and tissue-based B cells

Half-life elimination: Proportional to dose; wide ranges reflect variable tumor burden and changes in CD20 positive B-cell populations with repeated doses:

Following first dose: Mean half-life: 3.2 days Following fourth dose: Mean half-life: 8.6 days CLL: Median terminal half-life: 32 days NHL: Median terminal half-life: 22 days RA: Mean terminal half-life: 18 days GPA/MPA: 23 days

Excretion: Uncertain; may undergo phagocytosis and catabolism in the reticuloendothelial system

15.46 **Potential Drug Interactions:**

Increased Effect/Toxicity: Monoclonal antibodies may increase the risk for allergic reactions to rituximab due to the presence of HAC antibody. Antihypertensive medications may exacerbate hypotension.

Decreased Effect: Currently recommended not to administer live vaccines during rituximab treatment. Inactivated vaccines should be complete at least 2 to 4 weeks prior to starting therapy. rituximab may

diminish the effects of sipuleucel-T.

Immunosuppressants: rituximab may enhance the adverse/toxic effects of immunosuppressants, including:certolizumab pegol, pimecrolimus, tacrolimus, fingolimod, leflunomide, natalizumab, roflumilast,and to a lesser extent of denosumab,ophthalmic chloramphenicol, trastuzumab.

Myelosuppressants: rituximab may enhance the adverse/toxic effects of myelosuppressants, including: abatacept, belimumab, clozapine, deferiprone, dipyrone, promazine, and tofacitinib.

15.47 **Known potential adverse events:** Consult the package insert for the most current and complete information. Refer to the package insert pertaining to the following boxed warnings: Severe infusion reactions; Progressive multifocal leukoencephalopathy (PML); Tumor lysis syndrome leading to acute renal failure; and severe and sometimes fatal mucocutaneous reactions (lichenoid dermatitis, paraneoplastic pemphigus, Stevens-Johnson syndrome, toxic epidermal necrolysis and vesiculobullous dermatitis).

Common known potential toxicities, > 10%: Cardiovascular:

Peripheral edema, hypertension

Central nervous system: Fatigue, chills, neuropathy, headache, insomnia, pain

Dermatologic: Skin rash, pruritus, night sweats Endocrine & metabolic: Weight gain Gastrointestinal: Nausea, diarrhea, abdominal pain Hematologic: Lymphocytopenia, anemia, leukopenia, neutropenia, thrombocytopenia, cytopenia, febrile neutropenia

Hepatic: ALT increased Hypersensitivity: Angioedema Immunologic: Antibody development Infection: Infection, bacterial infection Neuromuscular & skeletal: Weakness, muscle spasm, arthralgia

Respiratory: Cough, rhinitis, epistaxis

Miscellaneous: Infusion related reaction, fever

Less common known potential toxicities, 1% - 10%: Cardiovascular:

Hypotension, flushing

Central nervous system: Dizziness, anxiety, migraine, paresthesia

Dermatologic: Urticaria

Endocrine & metabolic: Hyperglycemia, increased lactate dehydrogenase

Gastrointestinal: Vomiting, dyspepsia Infection: Viral infection, fungal infection

Neuromuscular & skeletal: Back pain, myalgia,

Respiratory: Dyspnea, throat irritation, bronchospasm, upper respiratory

tract infection, sinusitis

Rare known potential toxicities, <1% (Postmarketing and/or case reports):

Acute mucocutaneous toxicity, acute renal failure (associated with tumor lysis syndrome), acute respiratory distress, anaphylactoid reaction/anaphylaxis, angina pectoris, aplastic anemia, arthritis (polyarticular), bone marrow depression, bronchiolitis obliterans, cardiac

arrhythmia, cardiac failure, cardiogenic shock, encephalitis, fulminant hepatitis, gastrointestinal perforation, hemolytic anemia, hepatic failure, hepatitis, hypogammaglobulinemia (prolonged), hypoxia, increased serum immunoglobulins (hyperviscosity syndrome in Waldenstrom's macroglobulinemia), interstitial pneumonitis, intestinal obstruction, Kaposi's sarcoma (progression), laryngeal edema, lichenoid dermatitis, lupus-like syndrome, mucositis, myelitis, MI, nephrotoxicity, optic neuritis, pancytopenia, paraneoplastic pemphigus, pleurisy, pneumonia, pneumonitis, polymyositis, progressive multifocal leukoencephalopathy, pure red cell aplasia, reactivated pure red cell aplasia, reactivated tuberculosis, reactivation of HBV, reversible posterior leukoencephalopathy syndrome, serum sickness, Stevens-Johnson syndrome, supraventricular arrhythmia, toxic epidermal necrolysis, uveitis, vasculitis with rash, ventricular fibrillation, ventricular tachycardia, vesiculobullous dermatitis, viral reactivation (includes JC virus [PML], cytomegalovirus, herpes simplex virus, parvovirus B19, varicella zoster virus, West Nile virus, and hepatitis C), wheezing

15.48 **Drug procurement:** Investigational supply is provided free of charge to study participants by F. Hoffmann-La Roche.

F. Hoffmann-La Roche will supply investigational supply to McKesson. Each participating ACCRU treating location will order the drug from McKesson. Submit the Drug Order Request Form (found on the ACCRU web site) to:

McKesson

Each participating ACCRU treating location will be responsible for monitoring the supply of rituximab and will use the Drug Order Request Form to order additional supplies as needed.

Outdated or remaining drug is to be destroyed on-site as per procedures in place at each institution.

15.49a Temperature excursions that occur at the site should be reported by the site using the Genentech Temperature Excursion Form found on the ACCRU website for this study and emailed to:

Any shipment deviations (those not occurring at the site) should be reported to McKesson via email to:

15.49b Nursing Guidelines

Do not administer as an IV push or bolus since it increases the risk of a hypersensitivity reaction.

Hypotension, bronchospasms, and angioedema have occurred in association with Rituxan infusion. Because of this it is recommended that patients be pre-medicated with acetaminophen and diphenhydramine before infusion. Stop infusion for severe reaction. Infusion may be restarted at 50% rate after resolution of symptoms. It is recommended that diphenhydramine, acetaminophen, epinephrine, bronchodilators, IV saline, and corticosteroids are available for immediate use in the event of a hypersensitivity reaction during administration.

Patients should be cautioned to withhold their anti-hypertensive medication for 12 hours prior to drug administration.

Patients with preexisting cardiac conditions including arrhythmias and angina have had recurrences of these events during Rituxan therapy and should be monitored throughout the infusion and immediate post-infusion period.

It has been found that patients with bulky disease (lesion >10 cm in diameter) have an increased incidence of adverse events. Monitor for signs and symptoms of tumor lysis syndrome, and acute renal failure.

An infusion-related symptom complex consisting of fever and chills/rigors occurs in the majority of patients during the first infusion. These reactions generally occur within 30 minutes to 2 hours of beginning the first infusion and resolve with slowing or stopping the infusion and giving supportive care. The incidence of adverse reactions decreased from 80% to 40% with subsequent infusions.

Cytopenias are common and can be long term. Monitor CBC. Instruct patient to report signs and symptoms of infection, excessive bruising and/or bleeding to the health care team.

GI disturbances (Nausea, abdominal pain and less commonly diarrhea, vomiting, dyspepsia) headache, and weakness are common side effects. Treat as necessary. Monitor for effectiveness.

Adequate birth control measures should be used during therapy and for 12 months following therapy. Women should not breastfeed while drug is detectable in serum.

15.49c Endocrine and metabolic disturbances can be seen (hyper/hypoglycemia, hypocalcemia, hypocholesterolemia, hyperphosphatemia, hyperuricemia. Monitor labs and for signs or symptoms of these conditions. Treat accordingly.

16.0 Statistical Considerations and Methodology

16.1 Overview:

This is a single arm Phase II study of combination of polatuzumab vedotin, venetoclax

and rituximab and hyaluronidase human in patients with relapsed or refractory mantle cell lymphoma (MCL). The relapsed/refractory MCL patient population will include both ibrutinib-naive and ibrutinib-pretreated patients. An early safety analysis will be conducted in patients with B cell NHL who have relapsed or progressed after at least one line of therapy prior to continuing accrual in this phase II study.

16.11 Primary Endpoint: The primary endpoint of this trial is the complete response rate at the end of induction by PET-CT scans according to Lugano 2014. A complete response will be considered synonymous with "success", unless specified otherwise. All patients meeting the eligibility criteria, who have signed a consent form and have begun treatment, will be evaluable for response, unless they are determined to be a major violation.

16.2 Statistical Design

- 16.21 Decision Rule: The largest success proportion where the proposed treatment regimen would be considered ineffective in this population is 15%, and the smallest success proportion that would warrant subsequent studies with the proposed regimen in this patient population is 35%. The following one-stage design with an interim analysis is based on a two-stage Simon optimum design² and requires 46 evaluable patients to test the null hypothesis that the true success proportion in this patient population is at most 15%.
 - 16.211 Interim Analysis: Enter 16 evaluable patients into the study. If 3 or fewer successes are observed in the first 16 evaluable patients, we will consider this regimen ineffective in this patient population and terminate the study. Otherwise, if the number of successes is at least 4, we will continue accrual.
 - 16.212 Final Decision Rule: Enter an additional 30 evaluable patients into the study. If 10 or fewer successes are observed in the first 46 evaluable patients, we will consider this regimen ineffective in this patient population and terminate the study. Otherwise, if the number of success is at least 11, this will be considered evidence of promising activity and the treatment may be recommended for further testing in subsequent studies in this population.
 - 16.213 Over Accrual: If more than the target number of patients are accrued, the additional patients will not be used to evaluate the stopping rule or used in any decision-making process. Analysis involving over accrued patients is discussed in section 16.313.

NOTE: We will not suspend accrual at the interim analysis to allow the first 16 patients to become evaluable, unless undue toxicity is observed. Given the limited overall sample size and the inclusion of an AE stopping rule, we feel it is ethical to not halt accrual for the interim analysis. However, if accrual is extremely rapid, we may temporarily suspend accrual in order to obtain safety data on these patients before reopening accrual to further patients.

- 16.214 Dose de-escalation in safety analysis: A safety analysis will be performed in the first 6 evaluable patients per Section 16.4. In the case of unacceptable toxicity, the dose will be de-escalated. If this occurs, the first 6 patients will be evaluated separately and will not be included in any decision-making criteria.
- 16.22 Sample Size: The one stage design with an interim analysis to be utilized is fully described above. A minimum of 16 and a maximum of 46 evaluable patients with MCL will be accrued onto this phase II study unless undue toxicity is encountered. Patients with MCL treated at the final dose level in the early safety analysis will be included in phase II. If dose de-escalation is required during the safety analysis, an additional 6 evaluable patients will be accrued per section 16.4. We anticipate accruing an additional 5 (10%) patients to account for ineligibility, cancellation, major treatment violation, or other reasons for a total of up to 57 patients. If none of the six patients with B cell NHL enrolled in safety portion are MCL, the total sample size will be 63 patients.
- 16.23 Accrual Rate and Study Duration: The anticipated accrual rate is 2-3 evaluable MCL patients per month. At this rate, it will likely take about 2 years to enroll the patients. The maximum total study duration is expected to be approximately 5 years, or until the last patient accrued has been observed for at least 3 years. The earliest date anticipated for presentation of results is at approximately 2.5 years for the primary endpoint, or when the last patient accrued has been observed for at least 6 months.
- 16.24 Power and Significance Level: Assuming that the number of successes is binomially distributed, the significance level is .05, i.e. there is a 5% chance of finding the drug to be effective when it truly is not. The probability of declaring that this regimen warrants further study (i.e. statistical power) and the probability of stopping at the interim analysis under various success proportions can be tabulated as a function of the true success proportion as shown in the following table.

If the true success proportion is	0.15	0.20	0.25	0.30	0.35
Then the probability of declaring that the regimen warrants further studies is	0.049	0.212	0.467	0.700	0.851
And the probability of stopping at the interim analysis is	0.790	0.598	0.405	0.246	0.134

16.25 Other Considerations: AEs, quality/duration of response, and patterns of treatment failure observed in this study, as well as scientific discoveries or changes in standard care will be taken into account in any decision to terminate the study.

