Progress has been made in the treatment of MCL, however cure is still not attainable for most patients, and options to prolong remission and survival for relapsed patients remain limited. There is a need for the continued development of safe and effective therapies for patients with relapsed disease after front line therapy, and particularly for patients who relapse or progress on ibrutinib who have a dismal prognosis.

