2.2 Secondary Endpoints

- 2.21 To evaluate the EOI overall response rate (ORR) for the combination of RSc+Pola+Ven in relapsed/refractory MCL.
- 2.22 To evaluate the best response (CR, PR) in patients who continue on to maintenance therapy and evaluate the improvement in the depth of response.
- 2.23 To evaluate the progression free survival (PFS) and overall survival (OS) for the combination of RSc+Pola+Ven in relapsed/refractory MCL.
- 2.24 To compare the ORR, CR, PFS, and OS in ibrutinib refractory compared to ibrutinib naïve patients.

2.25 To evaluate regimen-related toxicity for patients treated with RSc+Pola+Ven.

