¹⁸ Subjects must return to the consenting ACCRU institution for CBC evaluation, or have outside laboratory CBC every 7 days during the first 6 weeks of therapy

¹⁹ Tissue is to be submitted no more than 30 days *after* registration. See Section 17.0 for more details.

^R Research funded

² Progressive disease is based on either PET-CT based or CT based response criteria

NOTE: A +/-14 day window is allowed for all survival follow-up visits.

5.0 Grouping Factors:

- 5.1 Cohort: Safety portion vs. expansion portion
- 5.2 Venetoclax Dosing Safety Lead-In: Dose 0 vs Dose -1
- 5.3 Previous ibrutinib exposure: ibrutinib naïve vs. ibrutinib pre-treated

NOTE: To ensure equal distribution of both ibrutinib naïve and pretreated patients at the dose level determined during the safety run-in, a minimum of 25 patients must be ibrutinib naïve. Therefore, accrual of ibrutinib pretreated patients will stop after 26 Ibrutinib pretreated patients are accrued

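### Does pooling ibrutinib-naive and pretreated patients, with no limit on the mix among the first 16, undermine the 15% v 35% test?

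*Combined protocol and SAP*

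**What the plan says.** Section 16.1 defines the population as mixed: "The relapsed/refractory MCL patient population will include both ibrutinib-naive and ibrutinib-pretreated patients". Section 16.21 gives that population a single null and a single target (35%). The 46 evaluable patients serve to "test the null hypothesis that the true success proportion in this patient population is at most 15" percent, with no CR rate by stratum and no assumed mix. Under Section 16.211 the study ends "If 3 or fewer successes are observed in the first 16 evaluable patients". Under Section 16.212, 11 or more CRs in 46 is promising. Section 16.311 limits the decision set by histology and dose level, not by ibrutinib status.

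Ibrutinib exposure is a grouping factor in Section 5.3, whose note opens "To ensure equal distribution of both ibrutinib" naive and pretreated patients. It sets a minimum of 25 naive patients and says that "accrual of ibrutinib pretreated patients will stop after 26 Ibrutinib pretreated patients are accrued". There is no minimum for pretreated patients and no ceiling for naive ones.

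Section 16.24 states its basis: "Assuming that the number of successes is binomially distributed, the significance level is .05". Its table gives power from 0.049 at a 15% CR rate to 0.851 at 35%, with an interim stop probability of 0.134 at 35%.

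**The concern.** The protocol treats the two strata as different. Section 1.4 stresses the need for new therapy "particularly for patients who relapse or progress on ibrutinib who have a dismal prognosis", and Section 2.24 plans "To compare the ORR, CR, PFS, and OS in ibrutinib refractory compared to ibrutinib" naive patients. If the CR rate differs by stratum, the chance of passing depends on who enrols as well as on the regimen.

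Two errors could follow:

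- A pretreated majority among the first 16 could trigger the futility stop for a regimen that meets 35% at an equal mix.
- A naive majority, which Section 5.3 does not limit, could carry a regimen that reaches only 15% at an equal mix past the 11 of 46 threshold.

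Section 5.3 names balance as its aim but enforces it from one side only, so this looks like a gap in the design.

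**Working it through.** **Inputs from the plan.** Stop at 3 or fewer CRs in 16; promising at 11 or more in 46; null 15%, target 35% (Sections 16.21–16.212). At most 26 pretreated and at least 25 naive (Section 5.3). Allowance of 5 extra patients (Section 16.22).

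**1. The plan's own table.** For a constant rate p, let X₁ ~ Bin(16, p) and X₂ ~ Bin(30, p). Then P(stop) = P(X₁ ≤ 3), and P(promising) = Σ over x = 4…16 of P(X₁ = x) · P(X₂ ≥ 11 − x).

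| True CR | 15% | 20% | 25% | 30% | 35% |
|---|---|---|---|---|---|
| P(promising) | 0.0486 | 0.2124 | 0.4672 | 0.6995 | 0.8506 |
| P(stop) | 0.790 | 0.598 | 0.405 | 0.246 | 0.134 |

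Every entry agrees with Section 16.24, so no stated figure is wrong.

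**2. What Section 5.3 secures.** 25 + 26 = 51 = 46 + 5. The pretreated cannot exceed 26 of the 46 decision patients. Since 26 is greater than 16, anything from 0 to 16 of the interim patients may be pretreated.

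**3. Sensitivity to the mix, regimen at 35% with an equal mix.** Replace each binomial by the sum of two, one per stratum, with rates centred on 35%. Each arriving patient is pretreated with probability q until 26 are pretreated; after that only naive patients enter. The stratum rates and q are assumptions. Cells show P(stop) / power.

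| CR pretreated / naive | q = 50% | q = 70% | q = 80% |
|---|---|---|---|
| 35 / 35 | 0.134 / 0.851 | 0.134 / 0.851 | 0.134 / 0.851 |
| 30 / 40 | 0.134 / 0.851 | 0.173 / 0.811 | 0.195 / 0.790 |
| 25 / 45 | 0.134 / 0.852 | 0.220 / 0.764 | 0.274 / 0.713 |
| 20 / 50 | 0.134 / 0.853 | 0.274 / 0.711 | 0.370 / 0.620 |
| 40 / 30 | 0.134 / 0.850 | 0.102 / 0.884 | 0.088 / 0.897 |

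The extreme that Section 5.3 allows is all 16 pretreated and 26 of 46 overall. With 25/45 it gives P(stop) 0.405 and power 0.588.

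**4. How likely an early excess is.** At q = 50%, 12 or more of 16 are pretreated with probability 3.8%. At q = 70% it is 45%.

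**5. The reverse risk, regimen at 15% with an equal mix.** With 9% pretreated and 21% naive, P(promising) is 4.7% at 8/16 and 23/46 pretreated, 12.6% at 4/16 and 12/46, and about 26% with none. With 12% and 18% it is 4.8%, 8.2% and 13.1%.

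**6. What forced balance would cost.**

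- *Interim set with at most 9 per stratum.* The expected number of presenting patients needed to fill the 16 is 17.5 at q = 50%, 23.7 at 70% and about 35 at 80%. At 80%, about 29 of those would be enrolled under the cap of 26, and there is a 64% chance that at least 30 are enrolled first. The wait beyond the first 16 is (35 − 16)/3 to (35 − 16)/2, or about 6–10 months at the 2–3 patients a month in Section 16.23.
- *Ceiling of 26 on naive patients.* This means at least 46 − 26 = 20 pretreated. If 30% of patients are pretreated, that takes 20/0.3 = 67 patients, or 22–33 months, against 46/3 to 46/2 = 15–23 months without the ceiling.

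**The case for a change.** The best case for a change is that the futility stop ends the study, the rule in Section 5.3 does not deliver the balance it names, and the cut-offs could stay as they are. The background section cites an overall survival of 3 months after progression on ibrutinib. Response is read 28–42 days after the last induction dose. With six 21-day cycles that dose falls on day 106, so the reading falls on about day 134–148. Early deaths and progressions count as non-CR, so a lower CR rate in such patients is plausible. With interim counts held to 7–9 per stratum and 20–26 of each in the 46, power under 25/45 would stay within 83–88%. Stating the mix behind 15% and 35% would cost almost nothing.

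The reading of the text stands: nothing controls the mix in the first 16. The size of the effect is not established. The survival figure is historical and concerns patients who progressed on ibrutinib, whereas Section 5.3 counts any exposure. Section 1.4 also links high CD79, the target of polatuzumab, to resistance to BTK inhibition, so even the direction of a CR gap is open. A cap on pretreated patients does not show that a pretreated majority is expected; the note gives equal distribution as its reason.

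The remedy is weakest where the problem would be worst. At an 80% pretreated share, most of the trial would probably be enrolled before a balanced interim set was filled. Response then takes more than four further months, and Section 16.213 does not suspend accrual. The futility look would protect few patients.

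**Conclusion.** The concern does not call for a change. A pooled single-arm test of a mixed population, with secondary comparisons by ibrutinib status, is a legitimate phase II design, and the table in Section 16.24 is correct for the constant rate it assumes. It also shows what a lower rate does: with 25/45 and early pretreated shares of 70% and 80%, the interim CR rate is 31% and 29%, and the 30% column already gives a stop probability of 0.246.

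The possible loss is real but conditional. Relative to 85%, at early pretreated shares of 70–80%, it is about 4–6 points of power with a 10-point CR gap, 9–14 with 20 points and 14–23 with 30 points. It is zero with no gap and becomes a gain if pretreated patients respond better. The gap and the share are both assumptions.

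The unstated mix is missing detail that analysts can handle in reporting. Ibrutinib status is recorded as a grouping factor, and Section 2.24 already lists CR among the outcomes to compare, so a reader will be able to judge the pooled result against the mix obtained. Balancing the interim set or capping naive patients would exchange one risk for slower accrual or a late futility look, a choice that belongs to the sponsor.
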